## 5. Study Population

### a) Treatments and subject enrolments

This study will be conducted in subjects presenting an acute ischemic stroke due to M1 occlusion, eligible for EVT based on neuro-interventionist and/or neurologist investigators' opinion.

Point of enrollment: "Patients are considered as enrolled only once the patient or if the patient is incapable of providing consent, once the patient's legally authorized representative has signed and dated the patient informed consent form as part of the informed consent process or confirmation of study participation by the individuals."

Subjects will undergo the EVT procedure in accordance with standard of care. CSGS will be inserted and up to 6 measurements will be done: 1 measurement distal to the access catheter in circulating blood (this is the reference measurement), 1 measurement proximal to the site of occlusion, 2 to 3 measurements inside the occlusion and 1 measurement at the most distal advancement of the guidewire (ideally distal to the occlusion). Each of these measurements will be tagged using the tablet interface.

The occlusion material recovered during the EVT will be immediately stored in a preservative solution of formaldehyde and sent to the histopathology lab for preparation. Analysis of histopathology of the occlusion will be conducted in a core central laboratory.

### b) Inclusion and exclusion criteria

#### *Inclusion criteria*

Candidates for the study must meet ALL the following inclusion criteria:

1. Age > 18 years
2. Clinical signs and symptoms consistent with the diagnosis of an acute ischemic stroke eligible for EVT based on neurointerventionist and/or neurologist investigators' opinion.
3. Occlusion with origin in M1 on CTA or MRA of an intracranial vessel amenable to EVT. Patients with migrated clots outside M1 will not be treated with the study device.
4. Written Informed Consent to participate in the study. If the subject is incapable of providing consent due to the patient's condition and the urgency of the EVT procedure, the Informed Consent Form will be obtained as per local country practice and approved by the Ethics Committee and Regulatory Agencies (if appl.)

#### *Exclusion criteria*

Candidates for this study will be excluded if ANY of the following conditions are present:

1. Patient has an intracranial occlusion that does not originate in M1 or/and tandem occlusions
2. Current participation in another investigational device or drug study that has not completed the primary endpoint or that clinically interferes with the current study endpoints.
3. Candidates not eligible for EVT based on neurointerventionist and/or neurologist investigators' opinion.

4. Known lactating or confirmation of positive pregnancy test according to site specific standard of care (e.g. test, verbal communication).

## 6. Statistical basis for sample size

The sample size calculation is driven by the amount of patients needed in the development and validation dataset. The size of the validation set is justified by the minimal number needed to achieve a sufficiently precise estimate of the primary endpoint, the precision being computed as the width of the confidence interval for a given confidence level.

The sample size calculation is split in two parts, one for the development set and one for the validation set.

### Development set size

The development set size was fixed to obtain a near-optimal RBC categorization performance (as defined in the primary performance endpoint), based on preliminary research performed by SENSOME on an ex-vivo dataset (DND\_tr-0033-clot-composition-phenomenological-model-development\_v1). The standard approach at Sensome was to use machine learning techniques to cope with the complexity of the signal. However, our accumulated experience guided the design of a phenomenological model (based on observations and on physical properties of the signal). Its performance on local-scale composition prediction, evaluated on the ex-vivo dataset, is comparable to the machine learning model performance previously developed. The fine-tuning of its parameters has got only a minor influence on the performance, as assessed on the ex-vivo dataset.

Its extrapolation for thrombectomy-like procedures requires an additional rule to distinguish the arterial wall and potentially a fine-tuning of handful of its parameters. Overall, the number of examples needed to complete the first local-scale clot composition prediction model is constrained by the observation of ideal cases (locally pure RBC content and locally pure platelets content). Based on the fraction of pure cases that was observed on the ex-vivo data set, and on rules to sub-sample this data set regarding the number of clot contact measurements per intervention, we find that  $N = 11$  is an adequate estimate of the development sample size.

We thus require a number of  $N_D = 11$  interventions with at least 1 evaluable measurement in contact with the clot to be included in the development set to reach near optimal performance with respect to primary performance endpoint assessment (Development Performance Population).

### Validation set size

The minimum number of  $N_V$  interventions to be included in the validation dataset to estimate the performance  $\hat{A}$  with sufficient statistical confidence margin is determined, with  $\hat{A}$  the area under the ROC curve (AUC) of the prediction model obtained on the validation sample of the population.

The following assumptions are made:

- **Estimated average number of independent individual measurements from a single tagged acquisition with clot contact = 5.44** (based on the quality check of data collected in the first 9 procedural successes)

- **Estimated average number of tagged acquisitions with clot contact per intervention = 3** (based on the quality check of data collected in the first 9 procedural successes)
- **Estimated number of RBC-positive cases = 53%** (based on the quality check of data collected in the first 9 procedural successes)
- **Expected number of RBC-negative cases = 47%**
- **An AUC of 0.85 is assumed with a maximal width of 0.1 for the 95% confidence interval**

With these assumptions, using the Hanley and McNeil estimate (Hanley and McNeil 1982) for the confidence interval to reach an expected AUC of 0.85 and a maximal width of the 95% confidence interval of 0.1, a number of  **$N_v = 14$  interventions** with at least 1 evaluable measurement valid interventions are necessary for the validation set (Local-Scale Performance Population).

### Total sample size

The total sample size has to be corrected for a 40% anomaly rate (see vi).

The **total sample size**  $N = (N_D + N_v)/0.60 = 42$ .

## 7. Bias

Since this is a single-arm study, no randomization is performed. Investigator, nor patients are blinded for the treatment.

To minimize bias, an independent Data Safety Monitoring Board (DSMB), also known as a Data Monitoring Committee (DMC), will be responsible for monitoring safety and performance aspects of the study. Rules of operation and responsibilities will be outlined in the DSMB Charter.

The DSMB consist out of an uneven number of experts in the field, enabling the assessment and conclusion with majority votes. If needed, the DSMB may invite ad hoc team members, such as statistical support. These ad-hoc members will refrain of voting. To review safety events happening in the study – for some events, the DSMB may be requesting additional information from the investigational site or the Core Lab to allow a comprehensive review. DSMB will be responsible of adjudicating the primary safety endpoint.

Secondly, to evaluate the Primary Performance Endpoint a binary classification of individual electrophysiological parameter measurements into 'RBC-positive' and 'RBC-negative' is performed by 2 Sensome experts independently. In case of discrepancies, a third expert will decide on the classification. This process cannot be performed by independent reviewers. Experts involved in annotating the development set shall not inspect the incoming validation dataset before the development is declared finished (the prediction models being fixed). As dataset inspection is also routine to detect anomalies, another Sensome expert not involved in the development could be designated in the transition period (when the development phase is not terminated but the development set is completed).

Thirdly, an expert in the field of histopathology from an independent Core Lab (Mayo Clinic) will perform the histopathological analysis of the clots. The Core Lab will be blinded for the results of the CSGS. Rules of operation and responsibilities are outlined in the Core Lab Instructions.

Fourthly, another independent imaging Core Lab (UCLA) will check the images. The imaging Core Lab will be set-up by 2 experienced readers. Both will check independently the pre-procedural, procedural and post-procedural images. Both readers will assess the primary safety endpoint. In case of disagreement between the 2 readers, a decision will be made by consensus. Rules of operation and responsibilities are outlined in the Core Lab Instructions.

It is well known that some clots might not be available for histological assessment. Next to that, data captured by the CSGS can be anomalous/missing. So the measures of agreement will only be based on those clots or on data from the CSGS that are available. The proportion of available clots is estimated to be approximately 60% of the total procedures. The proportion of available CSGS data is estimated to be 60% ([see 8.c.vi](#)). The possible bias introduced by this restriction cannot be assessed. It will be assumed that the performance of the medical device is not impacted by this selection bias.

Clinical study data will be monitored to verify its accuracy. Data Management will send out queries to the site in case of inconsistencies, contradictions, suspicious values or missing data.

## 8. Statistical analysis conventions

### a) Analysis Variables

The following variables will be collected by the investigator during the study visits in the **electronic CRF** (eCRF) and will be analysed by means of descriptive statistics:

- Informed consent data (date and time, by whom provided)
- Demographic data (age, gender, childbearing potential, race)
- Vital signs prior to the procedure (weight, height, heart rate, systolic and diastolic blood pressure determination, ECG), during and 24-hours post-procedure (heart rate, systolic and diastolic blood pressure)
- Physical examination prior to the procedure and 24 hours post-procedure (general appearance, cardiovascular, respiratory, skin, eyes, ears, abdomen, genitourinary, neurological, other)
- Timing of stroke onset and admission in hospital
- National Institutes of Health Stroke Scale (NIHSS) and Glasgow Coma Score prior to the procedure
- Medical history data (smoking, alcohol consumption, cardiac and non-cardiac)
- Baseline and 24 hours post-procedure blood laboratory evaluation (haematology, biochemistry, coagulation).
- Performed neuro imaging exams (date, type and findings)
- Eligibility to in- and exclusion criteria
- Timing during the intervention (tPA start (if applicable), anaesthesia start (if applicable), puncture, thrombus removal, revascularization, sheath removal, angio, fluoro, skin closure)
- Investigational, neurovascular and EVT devices used during the intervention (amount, type)
- Number of passes during the EVT intervention
- Procedural characteristics (timing) and events during EVT procedure
- CSGS performance (grading on 5-point Likert scale)
- Usability of CSGS (grading on 5-point Likert scale)
- Clot handling (timing and number of fragments)

- AE, SAE, SADE (diagnosis, seriousness, severity, timing, relationship to procedure/device/EVT, action taken and outcome)
- Concomitant medication (dose, type, frequency, indication, route, start and stop)
- Device Deficiencies (device, timing, description)
- Protocol violations (date and category)
- Suspected etiology
- Results pregnancy test (if applicable)
- Reason for early termination (if applicable)

The following variables will be collected at the histopathological Core Lab, entered in the eCRF and will be analysed by means of descriptive statistics:

- Clot composition (percentage RBC, WBC, fibrin and platelets and others): 3 slices will be analysed, one proximal, one in the middle of the clot and one distal. An average of the composition will be calculated.

The following variables will be collected at the imaging Core Lab and will be analysed by means of descriptive statistics:

- Vessel perforation and/or dissection due to the usage of CSGS comparing baseline imaging with procedural and post-procedural imaging (Non-contrast CT of the brain, CT Perfusion of the brain, Angiography of the brain, MRI of the brain), haemorrhage at baseline, final TICl, distal embolization and embolism in new territory.

## **b) Analysis Set(s)**

### Intention To Treat (ITT) Population

All patients who were enrolled, so all patients (or legally authorized representatives) who signed and dated the patient information consent form even though the CSGS was not used in the subject.

The safety analysis (amount of AE) will be performed on the intention to treat (ITT) population.

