**13.3 POINT OF ENROLMENT**

Point of enrolment: Patients are considered as enrolled once

1. The patient (or if the patient is incapable of providing consent, once the patient's legally authorized representative) has signed and dated the patient informed consent form as part of the informed consent process (or confirmation of study participation by the individuals mentioned in the NOTE under section: Informed Consent Process).
2. Patient's eligibility has been confirmed at the Investigational Site.  
Some subjects may be referred from other hospitals to undergo an Endovascular Thrombectomy. Prior to the transfer to the Investigational Site, the study patient may receive anti-thrombotic medication to dissolve the thrombus. This may mean that while a patient may be eligible when leaving the referral hospital, she/he no longer meets all eligible criteria at the treating (investigational) center.

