**Clinical investigation plan - CLOT OUT****15.2 ANALYSES POPULATION**

This study will be conducted in subjects presenting an acute ischemic stroke due to M1 occlusion, eligible for EVT based on neuro-interventionist and/or neurologist investigators' opinion.

Intention To Treat (ITT) Population

All patients who were enrolled, so all patients (or legally authorized representatives) who signed and dated the patient information consent form even though the CSGS was not used in the subject.

The **safety analysis** (amount of AE) will be performed on the intention to treat (ITT) population.

Treated Population

All patients in which the guidewire went through the sheath, even though if not all eligibility criteria were met or if a device failure occurred or if the clot could not be retrieved.

The **primary safety endpoint** will be determined on the Treated Population.

Per-protocol Population

All patients from the Treated Population who comply to all eligibility criteria.

No separate analyses will be performed for the per-protocol population.

Development Performance Population

This population includes patients from whom at least 1 evaluable acquisition was captured by the CSGS. An evaluable acquisition is defined as a "CLOT tag" or "Clot or beyond" tag with non-anomalous (see criteria section 15.6) impedance measurement. Data of this population will be used during the development phase to build the different models for classification of RBC-positive and platelet-positive.

Local-Scale Performance Population

This population includes patients for whom non-anomalous acquisition was collected by the CSGS during at least one tagged measurement with clot contact excluding patients from the Development Performance Population. Data of this population will be used during the validation phase to validate the model built during the development phase.

The analysis of the **primary performance endpoint** will be performed on data from the Local-Scale Performance Population.

Clot-Scale Performance Population

All patients from the Local-Scale Performance Population of which the clot could be retrieved for histological assessment.

Performance evaluation of the secondary performance endpoints related to the clot scale will be done on the Clot-Scale Performance Population.

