**Clinical investigation plan - CLOT OUT****15.6 MISSING DATA**

To assess the possible impact of missing data on the primary safety endpoint a sensitivity analysis will be conducted. Given the primary safety variable is a binary variable it is rather straightforward to assess the impact of different assumptions. In a worst case scenario all missing data are considered failures which will lead to the worst case scenario estimator of the proportion of perforations/dissections.

Regarding the impedance measurements captured by the CSGS, data might be missing or anomalous, having an impact on the performance endpoints. Based on the Device Deficiency rate obtained in the first 31 treated subjects, the estimated amount is 40%. This missingness/anomaly might be due to the following reasons:

- Technical malfunctions, leading to missing data or anomalous data, among which:
  - device anomaly caused by manufacturing anomaly
  - device anomaly due to electrical connection loss during navigation
- Use error, leading to:
  - missing data because measurements have not been tagged
  - anomalous data because the sensor was covered by the microcatheter while the measurement was tagged, as confirmed by the Imaging Core Lab on the angiography images corresponding to the tagged measurement.

The criteria to discard anomalous measurements due to technical malfunction include:

- Any acquisition associated with an error code raised by transmitter software (for instance due to loss of communication between sensor and transmitter) will be excluded from the development and validation datasets.
- Electrophysiological measurement from an electrode pair that shows a constant raw digital signal across acquisition frequencies (constant or piecewise constant with a single step) is considered anomalous and will be excluded.
- Electrophysiological measurement from an electrode pair that shows digital saturation consistently from REFERENCE to PRE-CLOT is considered anomalous; all remaining measurements made with this electrode pair will be excluded from the datasets.
- Anomalies related to invalid reference measurements are reported as too-high dispersion across electrode pairs in the 'REFERENCE' measurement. Persistence of the anomaly up to the 'PRE CLOT' measurement requires exclusion of all measurements from the concerned electrode pairs.

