### Treated Population

All patients in which the guidewire went through the sheath, even though if not all eligibility criteria were met or if a device failure occurred or if the clot could not be retrieved.

The primary safety endpoint will be determined on the Treated Population.

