## **xii. Safety analysis**

The primary safety endpoint (defined in 4) will be analysed in the Treated Population and presented in a table by means of descriptive statistics (count, percentages and 95% CI).

All Adverse Events will be classified with the Lowest Level Term (LLT) from the MedDRA dictionary (version 24.0, March 2021). All adverse events with onset during the study period will be displayed in summary tables for the ITT population. Tables will show the number of adverse events, the number and the percentage of patients affected by relation to usage of the device or the study procedure or to the EVT procedure (study procedure excluded) or underlying disease. Adverse events will be divided by seriousness. Severity, actions taken and outcome of the adverse events will be displayed in tables. Divisions will be made according to the timing of the event (during procedure, after procedure). All adverse events with descriptions of the event will be listed.

Technical events are defined as device or accessory malfunctions that are not associated with any clinical sequelae. All study site reported technical events will be summarized. The number and percentage of patients experiencing 1 or more technical events will be presented by the event description using counts and percentages. A detailed listing of a device deficiencies and malfunctions will be presented.

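### Adverse events are tabulated only on a consent-based ITT set, so device-related AE percentages are too low by the share of patients in whom the guidewire was never used

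*SAP*

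**What the plan says.** SAP 8.b: "The safety analysis (amount of AE) will be performed on the intention to treat (ITT) population". The ITT set consists of patients, or their representatives, "who signed and dated the patient information consent form even though the CSGS was not used in the subject". Protocol 15.2 has the same rule and the same inclusion of patients "even though the CSGS was not used in the subject".

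SAP 8.c.xii: "All adverse events with onset during the study period will be displayed in summary tables for the ITT population". The tables give event counts and "the number and the percentage of patients affected by relation to usage of the device", and likewise by relation to the study procedure, the EVT procedure and the underlying disease. SAP section 10 lists one AE table (Table 12).

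The exposed set is also defined, as the Treated Population: "All patients in which the guidewire went through the sheath, even though if not all eligibility criteria were met". The primary safety endpoint uses it (SAP 4.a and 8.b, protocol 15.2), and so do the demographic and baseline tables (SAP 8.c.x).

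Protocol 13.3 makes enrolment depend on consent and on a second condition: "Patient's eligibility has been confirmed at the Investigational Site". Protocol 15.2 and SAP 5.a and 8.b carry no eligibility condition.

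**The concern.** This is a first-in-human, single-arm device study. ITT is useful where a randomised comparison has to be protected, and there is none here. For AEs attributed to the device, ITT only adds people to the denominator who could not have had the event. The quantity of interest, the percentage of exposed patients harmed, would not appear in any planned AE table, and the AE percentages would have a different base from the primary safety endpoint and the baseline tables.

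The documents foresee untreated patients. Protocol 13.3 says a patient may lose eligibility after transfer, SAP 5.b says patients whose clot has migrated out of M1 will not receive the device, and SAP 8.b plans a listing of reasons for not undergoing the study procedure.

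The two meanings of enrolled leave it unclear whether screen failures count. Protocol 13.4 classes consented patients whose eligibility is not confirmed as screen failures, yet follows them for AEs until 24 hours after consent. Under the consent-only wording they enter the AE denominator, with a follow-up clock different from that of treated patients; under 13.3 they do not.

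**Working it through.** **Inputs.** Planned enrolment is up to 42 (protocol 9.1). The development set is 11, the validation set 14 and the anomaly rate 40% (protocol 15.5). At least 31 patients had been treated when the current documents were written (protocol 15.6, SAP 8.c.vi). The number enrolled but untreated, U, is not given and is varied below.

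**Plan's own figure.** With 3 × 5.44 measurements per intervention, a 53/47 split and AUC 0.85, the Hanley-McNeil 95% interval has width 0.103 at 13 interventions and 0.099 at 14, so 14 reproduces. Then (11 + 14)/0.60 = 41.67, rounded up to 42. The total reproduces; it serves here only as the denominator.

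**Device-related AEs.** Let T be the number treated and x the number of patients with a device-related AE. Assume such an AE needs the guidewire to have been used.

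- Treated percentage = x/T
- ITT percentage = x/(T + U)
- Relative understatement = 1 − T/(T + U) = U/(T + U)

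With T + U = 42, two events read 2/42 = 4.8% on ITT, and zero events have an upper limit of 8.4%. On the Treated Population:

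| Untreated U | Treated T | Understatement U/42 | Two events, 2/T | Zero events, upper 95% limit |
|---|---|---|---|---|
| 0 | 42 | 0% | 4.8% | 8.4% |
| 1 | 41 | 2.4% | 4.9% | 8.6% |
| 2 | 40 | 4.8% | 5.0% | 8.8% |
| 4 | 38 | 9.5% | 5.3% | 9.3% |
| 8 | 34 | 19.0% | 5.9% | 10.3% |
| 11 | 31 | 26.2% | 6.5% | 11.2% |

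The limits are two-sided 95% Clopper-Pearson. With zero events the upper limit is 1 − 0.025^(1/n), for example 1 − 0.025^(1/42) = 8.4%. The SAP plans no interval for AE percentages, so the method is my assumption.

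The ceiling U = 42 − 31 = 11 holds if every consented patient counts towards the 42. If 42 were treated and the untreated came on top, the understatement would be U/(42 + U): 4/46 = 8.7% for 4, and 14/56 = 25% for 14.

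**AEs that do not need the device.** ITT percentage = (T × p_treated + U × p_untreated)/(T + U). Assume p_treated = 30%, T = 38 and U = 4:

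- p_untreated = 0%: 11.4/42 = 27.1%
- p_untreated = 15%: 12.0/42 = 28.6%
- p_untreated = 30%: 12.6/42 = 30.0%
- p_untreated = 50%: 13.4/42 = 31.9%

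The ITT figure can lie below, at or above the Treated figure.

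**The case against.** The strongest reply is that little is lost. The main device harm, perforation or dissection due to the guidewire, already has the Treated denominator. Event counts are not diluted. The disposition table gives the numbers enrolled and the numbers who underwent the study procedure, and the SAP listings give every AE and each patient's analysis sets, so with about 42 patients anyone can rebuild Treated-set rates. All of this is true and limits the harm. It does not correct the one AE table that is planned and will be quoted.

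A second reply also stands. The study procedure starts at tablet preparation (protocol 13.8 and 17.3), so a study-procedure-related AE can precede sheath passage. ITT keeps such an event in the main table; a bare switch to Treated would lose it. Moving device deficiencies to Treated would likewise drop failures before insertion. The fix has to allow for both.

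Third, the size rests on an assumed U. With 31 already treated, 11 untreated of 42 would mean that nobody after those 31 received the device, so it is an extreme. At 1 to 4 untreated, two events read 4.8% on ITT against 4.9% to 5.3% on Treated.

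A reader might infer more than the documents support:

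- That every AE percentage is diluted. The last calculation shows otherwise for AEs that can occur without the device.
- That the 40% anomaly rate measures non-use. It describes missing or anomalous sensor data among treated subjects.
- That the DSMB looks at 5 and 20 patients would fall short of that many exposures, since the protocol keys them to enrolment and the SAP to treatment. With 31 treated, both points had been passed, and the suspension triggers are event counts, not percentages.
- That untreated patients put the 25 evaluable interventions at a calculable risk. The documents give no non-use rate, and the 31 patients who supplied the 40% are already observed, so they cannot be treated as future draws.

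**Conclusion.** The point holds for device-related AEs. The planned tables understate the percentage of exposed patients affected by exactly the untreated share of ITT: 2.4% to 26% in relative terms for 1 to 11 untreated of 42, and nothing if all are treated. With zero events, the upper 95% limit would be stated as 8.4% when the exposed sample supports 9.3% (38 treated) or 11.2% (31 treated). This rests on an assumed number untreated, on Clopper-Pearson limits, and on device-related AEs requiring use of the guidewire.

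For all-cause, EVT-related and disease-related AEs, the defect is that exposed and unexposed patients are mixed; no direction of bias can be claimed. The inconsistent definition of enrolled is a separate defect in the text, and it leaves the AE denominator undefined for consented screen failures. The absolute differences are probably small, but the change is easy and gives the rate that a first-in-human device study should report.

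**What to change.** - In SAP 8.b, SAP 8.c.xii, SAP Table 12 and protocol 15.2, make AE, SAE and SADE counts and percentages on the Treated Population the main tables.
- Add a separate column for consented but untreated patients, including any study-procedure-related AE before sheath passage, so that no event is lost.
- Keep device deficiencies reported for all devices opened or used, including failures before insertion.
- Use one definition of enrolled in protocol 13.3, protocol 15.2, SAP 5.a and SAP 8.b, and say explicitly whether consented screen failures enter any AE denominator.

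The cost is wording and table shells, with no new data. AE percentages may rise slightly and the table gains one column. The SAP is to be finalised before database lock, which is the time to make the change.
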